 - **Phase 2:** 24 weeks (8 cycles)
- **Phase 1b and 2 Extension Phase:** Subjects will continue to receive study treatment until disease progression, development of unacceptable toxicity, subject choice, withdrawal of consent, completion of 35 treatments (approximately 2 years) with pembrolizumab, lost to follow up or discontinuation of this study by the sponsor. Subjects who discontinued pembrolizumab for any reason and are still receiving lenvatinib study drug, will be transitioned to commercial lenvatinib if local country regulations permit.

Efficacy Assessments:

Tumor assessments will be performed by the investigators based on both irRECIST and modified RECIST 1.1. Treatment decisions by the investigator will be based on irRECIST. All scans for tumor assessments performed during the study should be archived in accordance with the standard local practice. The Scans from Phase 1b must be accessible in the event of a sponsor request to submit them for central review. For Phase 2, images acquired for tumor assessments will be sent to an imaging core laboratory (ICL) for archiving and potential independent analysis. As of Amendment 3, tumor assessment scans for the EC subjects will be assessed by IIR. As of Amendment 5, tumor assessment scans for the renal cell carcinoma subjects will also be assessed by IIR. As of Amendment 08, for subjects enrolled in the RCC cohort who were previously treated with anti-PD-1/PD-L1 mAb, available pre-Baseline scans that demonstrate previous progression, will be collected by sites and sent to an ICL designated by the sponsor for quality assessment and archival, and potential future independent review.

As of Amendment 08, scans acquired after data cutoff for final efficacy analysis, in any cohort, will no longer be sent to the imaging core lab. As of Amendment 09, pre-baseline scans for RCC subjects are not required.

Tumor assessments will be carried out during the Pretreatment Phase and then every 6 weeks (during the sixth week; counting from C1D1) until Week 24, then every 9 weeks during treatment cycles in both the Treatment Phase and the Extension Phase. As of Amendment 09, tumor assessments will continue during the Extension Phase as per local standard of care but not less frequent than every 6 months. Tumor assessments will not be collected during the Follow-Up period of the Extension Phase. Magnetic resonance imaging /MRI scans of chest, abdomen, and pelvis and of other known sites of disease will be obtained at Screening (within 28 days prior to Cycle 1 Day 1), at all tumor assessment time points, and as indicated clinically and as per local standard of care. Color photographs containing a millimeter scale must be taken of all skin lesions being used as target lesions. Historical standard of care scans that are performed with scanning parameters consistent with the requirements for this protocol within 28 days prior to dosing are acceptable. Subjects with squamous cell carcinoma of the head and neck must also have head and neck scans performed.

Magnetic resonance imaging may be used instead of CT for head, neck, abdomen, and pelvis; however, the chest must be assessed using CT. Chest disease may not be followed using chest x-ray.

A brain scan (CT with contrast or MRI pre- and post-gadolinium) must be performed at Screening to assess potential central nervous system (CNS) disease and/or metastases. For subjects with previously treated eligible brain metastases, a brain scan must be performed at all tumor assessment time points. For all subjects, a follow-up brain scan must be performed to confirm immune-related complete response (irCR) within 1 week of response confirmation, or if clinically indicated.

The tumor assessment schedule should not be affected by interruptions in study treatment.

Subjects going Off-Tx without disease progression will also undergo tumor assessments per the Schedule of Procedures/Assessments until disease progression is documented or another anticancer therapy is initiated.

The same method of assessment must be used at all-time points as was used at Screening.

Throughout the study it is critical that the same imaging methodology be applied and contrast be consistently provided unless IV contrast becomes medically contraindicated during the course of treatment or the dose of contrast needs to be adjusted based on the subject's health status.

Bone scans will be performed at Screening, every 24 weeks, or sooner if clinically indicated, and at confirmation of irCR (except for subjects with squamous cell carcinoma of the head and neck). Lesions identified on bone scans must be verified and followed with correlative cross-sectional imaging.

In order for immune-related stable disease (irSD) to be considered the best overall response, it must occur ≥ 5 weeks following the first dose of study drug.

The first radiological assessment of tumor response status will be performed at Week 6 (± 1 week), unless there is clinical indication warranting earlier radiologic imaging. If imaging at Week 6 shows irSD, treatment will be continued and tumor assessments will be conducted at the next regularly scheduled imaging time point, ie, at Week 12 (± 1 week). Responses (irPR [PR] or irCR) should be confirmed no less than 4 weeks after the initial response, but generally at the next scheduled tumor assessment time point.

If the time point tumor assessment is PD, treatment should continue and tumor assessments be repeated at least 4 weeks later, but generally at the next scheduled tumor assessment time point in order to confirm immune-related progression disease (irPD). If repeat imaging shows a reduction in the tumor burden compared to the initial tumor assessment demonstrating PD, treatment may be continued as per treatment schedule. If repeat imaging confirms irPD, subjects will be discontinued from study treatment. In determining the tumor time point response, investigators should consider all target lesions as well as nontarget lesions and new lesions. The decision to continue study treatment after the first evidence of PD is at the investigator's discretion based on the clinical status of the subject.

Subjects may continue receiving study treatment while waiting for confirmation of PD if they are clinically stable as defined by the following criteria:

- Absence of signs and symptoms (including worsening of laboratory values) indicating disease progression
- No decline in ECOG PS
- Absence of rapid progression of disease
- Absence of progressive tumor at critical anatomical sites (eg, cord compression) requiring urgent alternative medical intervention

If irPD is confirmed and the subject is experiencing extraordinary clinical benefit, the site must contact the sponsor to discuss continuing treatment.

Tumor assessments per modified RECIST 1.1 will follow [Eisenhauer, et al. \(2009\)](#); however, up to 10 target lesions, up to 5 per organ, may be selected (as opposed to a maximum of 5 target lesions, up to 2 per organ).

Pharmacokinetic:

Plasma concentrations of lenvatinib will be measured.

Dose-normalized PK profile for lenvatinib in combination with pembrolizumab from this study will be compared graphically to that from patients with different tumor types from completed studies of those receiving lenvatinib monotherapy.

Pharmacodynamic/Pharmacogenomic:

Blood and Tissue Biomarkers: Blood samples for the development of exploratory predictive biomarkers will be collected prior to the first dose of study drug, on Cycle 1 Day 15, and on D1 of all subsequent cycles during Treatment Phase, and at the Off-Tx assessment. Subjects will be required to provide an archival tumor tissue sample and/or a fresh biopsy of tumor before treatment for biomarker analyses (patients with inaccessible tumors for biopsy specimens can be enrolled without a biopsy upon consultation and agreement by the sponsor). For subjects in the NSCLC

cohort every effort is to be made to obtain a fresh biopsy of tumor at the beginning of Cycle 2 (optional for other cohorts on study) if they have recovered adequately from the biopsy taken prior to starting therapy and to provide the acquired tissue for these biomarker analyses. Biomarker discovery and/or validation will be performed to identify blood or tumor biomarkers that may be useful to predict subject response to lenvatinib and/or pembrolizumab, as determined by evaluation of response-related and/or safety-related outcomes as well as for potential use in diagnostic development. Blood samples from subjects receiving lenvatinib and pembrolizumab may be analyzed using global proteomic methods, enzyme-linked immunosorbent assay (ELISA), multiplex bead-based immunoassay, or other assays/methods or new technology. In addition, biomarkers identified in other lenvatinib clinical studies may also be assessed in the biomarker samples collected from subjects enrolled in this study. The decision to perform exploratory biomarker analysis may be based on the clinical outcome of this study and/or the signals observed in other clinical studies or other information available at that time.

Archived, formalin-fixed paraffin-embedded (FFPE) tissue or a newly obtained biopsy will be collected from all subjects for potential assessment of mutations and other genetic alterations and/or proteins including PD-1/PD-L1 status and other relevant biomarkers (eg, tumor infiltrating lymphocytes, T-cell repertoire, ribonucleic acid [RNA] signature profiles) which may be important in the development and progression of cancer as well as for potential use in diagnostic development. Appropriate technology/methodologies will be used based on the amount of tumor tissue available.

For all tumor types except NSCLS, optional fresh paired tumor biopsies will be collected from consented subjects to examine markers including markers of target engagement, relevant pharmacodynamic biomarkers, and potential markers of response. Fresh biopsies should be limited to readily accessible tumor lesions (eg, skin, peripheral lymph nodes, liver metastases that can be readily accessed using CT guidance). Subjects should have the biopsy before administration of the first dose of study drug and at a time point 3-6 weeks after the first dose (if they have recovered adequately from the biopsy taken prior to starting therapy). For NSCLC, every effort is to be made to obtain a fresh tumor biopsy; subjects will have fresh tumor biopsies collected from consented subjects before administration of the first dose of study drug and at a time point 3-6 weeks after the first dose (if they have recovered adequately from the biopsy taken prior to starting therapy).

A blood sample for peripheral blood mononuclear cells and plasma isolation will be collected from enrolled subjects. Cell free nucleic acid isolated from plasma samples may be used to obtain circulating tumor DNA (ctDNA) and explore tumor genetic alterations such as mutations observed in archival tumor samples as well as those which develop during drug treatment.

In Phase 2, as of Amendment 4, a blood sample for nucleic acid analysis will be collected for potential assessment of gene expression profiling. In Phase 2, as of Amendment 3, a blood sample will be collected for potential pharmacodynamics and pharmacogenomics analysis. Variation in lenvatinib exposure or the occurrence of AEs observed in the study population may be evaluated by correlating single-nucleotide polymorphisms with PK, safety, or pharmacodynamic data. Genomic DNA extracted from blood samples may be used to confirm whether the DNA sequence variants observed in DNA extracted from tumor material are limited to the tumor, for potential microsatellite instability analysis, and for potential immune response monitoring.

As of Amendment 06, available known mutation status including mismatch repair (MMR) or microsatellite instability (MSI) status will be collected on the case report form.

Data obtained will be used for research to assist in developing safer and more effective treatments and will not be used to change the diagnosis of the subject or alter the therapy of the subject. The DNA will not be used to determine or predict risks for diseases that an individual subject does not currently have. Any sample or derivatives (DNA, RNA, and protein) may be stored for up to

15 years to assist in any research scientific questions related to lenvatinib/pembrolizumab, cancer, and/or for potential diagnostic development.

Instructions for the processing, storage, and shipping of samples will be provided in the Laboratory Manual.

Safety:

Safety assessments will consist of monitoring and recording all AEs and serious adverse events, using Common Terminology Criteria for Adverse Events (CTCAE) v. 4.03; regular laboratory evaluation for hematology, blood chemistry, and urine values; regular performance of physical examinations (including oral examinations), periodic measurement of vital signs, and ECGs.

Bioanalytical Methods

Lenvatinib will be quantified using validated HPLC-tandem mass spectroscopy method.

Statistical Methods

Study Endpoints

ORR_(Week 24) is defined as the proportion of subjects who have best overall response (BOR) of irCR_(Week 24) or irPR_(Week 24) as of the Week 24 tumor assessment time point.

ORR is defined as the proportion of subjects who have BOR of irCR or irPR at the time of data cutoff.

PFS is defined as the time from the first study dose date to the date of first documentation of confirmed disease progression or death (whichever occurs first).

OS is measured from the start date of the treatment period until date of death from any cause. Subjects who are lost to follow-up and the subjects who are alive at the date of data cutoff will be censored at the date the subject was last known alive.

DCR is defined as the proportion of subjects who have BOR of irCR or irPR or irSD (duration of irSD \geq 5 weeks).

CBR is defined as the proportion of subjects who have BOR of irCR or irPR or durable irSD (duration of irSD \geq 23 weeks).

DOR is defined as the duration of irCR or irPR.

Durable SD rate is defined as the proportion of subjects whose BOR is irSD and the duration of irSD is \geq 23 weeks.

As exploratory analyses, tumor response endpoints will be evaluated for the subjects in the endometrial and renal cell carcinoma analysis sets using the IIR assessments.

Analysis Sets:

Safety Analysis Set will include all subjects who received any amount of study drug. This will be the analysis set for all safety evaluations.

MTD Analysis Set will include all subjects who completed Cycle 1 of treatment of Phase 1b or discontinued early due to DLT. This will be the analysis set to determine MTD.

Full Analysis Set (Intent-to-Treat [ITT] Analysis Set) will include all subjects who entered the study treatment period.

PK Analysis Set: All the subjects who have received at least 1 dose of lenvatinib and have evaluable concentration data.

Pharmacodynamic Analysis Set will include all subjects who have received at least 1 dose of study drug (lenvatinib or pembrolizumab) and have evaluable pharmacodynamic data.

Endometrial Carcinoma Analysis Set: will include all EC subjects from Phase 1b and Phase 2.

Renal Cell Carcinoma Analysis Set will include all renal cell carcinoma subjects from Phase 1b and Phase 2.

Non-Small Cell Lung Cancer Analysis Set will include all NSCLC subjects from Phase 1b and Phase 2.

Melanoma Analysis Set will include all melanoma subjects from Phase 1b and Phase 2.

Efficacy Analyses

Selected efficacy analyses may be performed if needed for subjects with the combination of lenvatinib and pembrolizumab as the first line treatment versus other subjects with prior systemic therapies. For the renal cell carcinoma cohort, efficacy subgroup analyses may be presented for treatment naïve subjects, subjects who were previously treated with an anti-PD-1/PD-L1 therapy, and subjects who were previously treated without an anti-PD-1/PD-L1 therapy.

Analysis of Primary Endpoint for Phase 1b:

The primary objective of Phase 1b is to determine the DLTs, MTD, and to establish the RP2D. The efficacy endpoints in Phase 1b will be summarized and listed by dose level based on the Safety Analysis Set. No statistical comparison will be performed.

Analysis of Efficacy Endpoints for Phase 2:

Efficacy analyses will primarily be based on the Full Analysis Set. Efficacy (eg, $ORR_{(Week\ 24)}$, ORR, BOR during the Treatment and Extension Phases, PFS, DCR, durable SD, CBR) will be assessed by irRECIST and modified RECIST 1.1. The efficacy endpoints will be summarized and listed by cohort. No statistical comparison will be performed.

Analysis of Primary Efficacy Endpoint for Phase 2:

The primary efficacy endpoint in Phase 2 is ORR as of Week 24 ($ORR_{(Week\ 24)}$) based on irRECIST based on the Full Analyses Set. Estimated $ORR_{(Week\ 24)}$ and the exact 95% confidence intervals (CI) using the method of Clopper–Pearson will be presented. The primary efficacy analysis will be performed when all subjects in the same cohort have completed 8 cycles of treatment, discontinued due to disease progression, developed unacceptable toxicity, withdrew consent, or the study is terminated by the Sponsor.

Analysis of Secondary Efficacy Endpoints for Phase 2:

The secondary efficacy endpoint will be OS, PFS, DCR, CBR, DOR, and durable SD ($SD \geq 23$ weeks) by irRECIST as appropriate.

Median time to PFS and 95% CI will be provided for the data from this study by cohort as well as historical control data if available, and PFS will be analyzed using Kaplan–Meier (KM) product-limit estimates along with KM plots. Three-month, 6-month, 9-month and 1-year PFS rates will be estimated from KM and corresponding 95% CI will be calculated.

Median survival time and the 95% CI, the survival rates at 12, 18 and 24 months will be calculated using KM product-limit estimates for each cohort and presented with 2-sided 95% CIs. KM plots for OS will be provided.

Disease Control Rate, CBR, and durable SD rate will be provided with exact 95% CI using the method of Clopper and Pearson.

Analysis of Exploratory Efficacy Endpoints:

The tumor response endpoints will be explored based on modified RECIST 1.1 assessments, and will be summarized and listed by cohort. No statistical comparison will be performed between irRECIST and modified RECIST 1.1 results.

The tumor response endpoints will also be evaluated for the subjects in the endometrial and renal cell carcinoma analysis sets using IIR assessment using irRECIST, modified RECIST 1.1 and RECIST 1.1 as exploratory analyses. A concordance analysis will be performed comparing IIR and investigator assessments.

Pharmacokinetic and/or Pharmacodynamic Analyses

Pharmacokinetic:

To assess any drug–drug interaction between lenvatinib and pembrolizumab, the dose-normalized PK profile for lenvatinib in combination with pembrolizumab from this study will be compared graphically to that from patients with different tumor types from completed studies of those receiving lenvatinib monotherapy.

Pharmacodynamic:

The effect of lenvatinib-pembrolizumab combination therapy on soluble, tissue, genetic and/or imaging biomarkers will be summarized using descriptive statistics using the pharmacodynamic analysis set.

Safety Analyses:

Safety analyses will be performed on the Safety Set. Safety data will be summarized using descriptive statistics. Categorical variables will be summarized by number and percentage. Continuous variables will be summarized using n (number of subjects with available data), mean, standard deviation (SD), median, and range (minimum and maximum) unless otherwise specified. Laboratory test results will be summarized using 3 categories, hematology, liver and renal, and other clinical chemistry. Hematology and clinical chemistry parameters that are graded by CTCAE v 4.03 will be summarized by CTCAE grade. Shifts from baseline to the worst CTCAE grade will be tabulated.

Selected safety analyses may be performed if needed for subjects with the combination of lenvatinib and pembrolizumab as the first line treatment versus other subjects with prior systemic therapies. For the renal cell carcinoma cohort, safety subgroup analyses may be presented for treatment naïve subjects, subjects who were previously treated with an anti-PD-1/PD-L1 therapy, and subjects who were previously treated without an anti-PD-1/PD-L1 therapy.

Sample Size Rationale

Phase 1b: A sample size of 10 to 30 subjects will be enrolled to assess MTD. This is not based on statistical power considerations.

Phase 2: A sample size of 10 evaluable subjects will be enrolled per cohort, with the possibility of expansion to 20 evaluable subjects per cohort, depending on the evaluation by the sponsor and investigators of the efficacy and safety results observed with the initial 10 evaluable subjects in each cohort.

As of Amendment 3, the EC cohort may be further expanded to approximately 120 evaluable subjects. For this expansion decision, 2 interim analyses will take place when 21 and 60 subjects have sufficient follow-up to be evaluated for response. The decision to expand enrollment will be based on the results of 2 interim analyses, which will spend $\beta=0.012$ and $\beta=0.024$ at the first and second interim analyses, respectively. Based on an assumption of H_0 : 16% ORR and H_1 : 34% ORR, at 2-sided $\alpha=0.02$, this design will give 97% statistical power with 120 subjects. At the first interim analysis ($N=21$), if there are more than 3 responses, then approximately 40 additional subjects will be enrolled. At the second interim analysis ($N=60$), if there are more than 12 responses, approximately 60 additional subjects will be enrolled. If there are 12 or fewer responses, the sponsor may decide whether to expand enrollment based on clinical outcome, eg,

ORR and DOR. If the expansion beyond 60 subjects does not happen, this design for the EC cohort has approximately 86% power at 2-sided $\alpha = 0.02$.

As of Amendment 7, the renal cell carcinoma cohort may be further expanded to approximately 145 total evaluable subjects to allow for approximately 100 evaluable subjects who have received 1 or 2 prior therapies that included an anti-PD-1/PD-L1 mAb. The decision to expand enrollment will be based on the results of 2 interim analyses. The first interim analysis will take place when 22 subjects (11 treatment naïve and 11 previously treated without an anti-PD-1/PD-L1 mAb) have sufficient follow-up to be evaluated for response. At the first interim analysis ($N = 22$), if there are more than 5 responses, then approximately 45 additional subjects will be enrolled. It is anticipated that the additional 45 subjects will consist of approximately 12 treatment naïve subjects enrolled under Amendment 5 and approximately 33 previously treated subjects who have received 1 or 2 prior therapies and have progressed on treatment with an anti-PD-1/PD-L1 mAb. The second interim analysis will include these 45 additional subjects and the 11 treatment naïve subjects included in the first interim analysis and will take place when these 56 subjects have sufficient follow-up to be evaluated for response. At the second interim analysis, whether the previously treated renal cell carcinoma subset will be further expanded will be decided based on clinical review of both efficacy and safety data.

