Grade 3 is defined as ANC <1000/mm³ with a single temperature of >38.3 °C (101 °F) or a sustained temperature of ≥38 °C (100.4 °F) for more than one hour.
Grade 4 is defined as ANC <1000/mm³ with a single temperature of >38.3 °C (101 °F) or a sustained temperature of ≥38 °C (100.4 °F) for more than one hour, with life-threatening consequences and urgent intervention indicated

Only toxicities with a clear alternative explanation (eg, due to disease progression) or transient (≤72 hours) abnormal laboratory values without associated clinically significant signs or symptoms based on investigator determination can be deemed a non-DLT.

All subjects enrolled in Phase 1b will be assessed for DLTs during the DLT assessment window of Cycle 1 (Treatment Phase). Subjects who discontinue study treatment prior to completing the Treatment Phase for any reason other than DLT will be replaced. Once they complete the Treatment Phase, each subject still receiving study treatment will transition into the Extension Phase. Tumor assessments will continue during the Extension Phase. As of Amendment 09, tumor assessments will continue during the Extension Phase as per local standard of care but not less frequent than every 6 months. Tumor assessments will not be collected during the Follow-Up period of the Extension Phase.

Phase 2 - Expansion:

After the MTD is confirmed, and depending on the safety and efficacy observed, 6 cohorts will be enrolled. Each of these cohorts will enroll subjects with only 1 type of tumor (ie, NSCLC, predominantly clear cell renal cell carcinoma, EC, UC, melanoma (excluding uveal melanoma), or squamous cell carcinoma of the head and neck). Lenvatinib in combination with pembrolizumab will be administered at the RP2D. The intent is to enroll 20 subjects in each of the 6 cohorts, with possible expansion of enrollment in the endometrial and renal cell carcinoma cohorts. For all 6 cohorts, data from the first 10 subjects in each cohort will be reviewed by the sponsor and investigators. At least 3 subjects must show responses in order to determine continued enrollment to 20 evaluable subjects.

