Amendment 09, tumor assessments will continue during the Extension Phase as per the local standard of care but not less frequent than every 6 months. Tumor assessments will not be collected during the Follow-Up period of the Extension Phase.

Phase 2 – Expansion:

Subjects will be assigned by tumor type into 1 of 6 cohorts (minimum of 10 or 20 evaluable subjects per cohort) to receive the MTD, which was established as the RP2D in the Phase 1b portion of this study (lenvatinib 20 mg/day orally + pembrolizumab 200 mg Q3W, IV) to assess the safety and efficacy of the combination in the selected tumor-types. Each cohort will consist of subjects with one of the tumor types listed in the Phase 1b section above. Phase 2 is illustrated in [Figure 2](#).

After the MTD is confirmed, and depending on the safety and efficacy observed, 6 cohorts will be enrolled ([Figure 2](#)). Each of these cohorts will only enroll subjects with one type of tumor (ie, NSCLC, predominantly clear cell RCC, EC, UC, melanoma (excluding uveal), HNSCC). RP2D combination doses will be administered. The intention is to enroll 20 subjects in each of the 6 cohorts. Data from the first 10 subjects in each cohort will be reviewed by the sponsor and investigators. At least 3 subjects must show response in order to determine continued enrollment up to 20 subjects.

The EC cohort may be further expanded to approximately 120 evaluable subjects. The decision to expand enrollment will be based on the results of 2 interim analyses that will take place when 21 and 60 subjects have sufficient follow-up to be evaluated for response. At the first interim analysis (N = 21), if there are more than 3 responses, then approximately 40 additional subjects will be enrolled. At the second interim analysis (N = 60), if there are more than 12 responses, approximately 60 additional subjects will be enrolled. If there are 12 or fewer responses, the sponsor may decide whether to expand enrollment based on clinical outcome, eg, ORR and DOR.

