9.7.2 Determination of Sample Size

Phase 1b – Determination of the Maximum Tolerated Dose

The total number of subjects required for the Phase 1b portion of this study will depend upon the toxicities observed as the study progresses. A sample size of approximately 10 to 30 subjects in Phase 1b will be enrolled to assess MTD. This is not based on statistical power considerations.

Phase 2 – Expansion in Selected Tumor Types

A sample size of 10 evaluable subjects will be enrolled per cohort, with the possibility of expansion to 20 evaluable subjects per cohort, depending on the evaluation by the sponsor and investigators of the efficacy and safety results observed with the initial 10 evaluable

subjects in each cohort. For a reference of the precision of ORR estimates in all cohorts except the EC and the renal cell carcinoma cohorts, the associated 2-sided 95% CIs for the ORR of 10% to 90% for both 10 subjects and 20 subjects, per cohort are provided in Table 10.

The EC cohort may be further expanded to approximately 120 evaluable subjects. The decision to expand enrollment will be based on the results of 2 interim analyses which will spend $\beta=0.012$ and $\beta = 0.024$ at the first and second interim analysis, respectively. Based on an assumption of H_0 : 16% ORR and H_1 : 34% ORR, at 2-sided $\alpha = 0.02$, this design will give 97% statistical power with 120 subjects. At the first interim analysis ($N = 21$), if there are more than 3 responses, then approximately 40 additional subjects will be enrolled. At the second interim analysis ($N = 60$), if there are more than 12 responses, approximately 60 additional subjects will be enrolled. If there are 12 or fewer responses, the sponsor may decide whether to expand enrollment based on clinical outcome, eg, ORR and DOR. If the expansion beyond 60 subjects does not happen, this design for the EC cohort has approximately 86% power at 2-sided $\alpha= 0.02$. The boundaries for the decision to expand enrollment in the endometrial cohort are presented in [Table 11](#).

Table 10 2-sided 95% Confidence Interval for the ORR of 10% to 90% (10 subjects and 20 subjects)

ORR (N=10)	95% CI
10%	(0.003, 0.445)
20%	(0.025, 0.556)
30%	(0.067, 0.653)
40%	(0.122, 0.738)
50%	(0.187, 0.813)
60%	(0.262, 0.878)
70%	(0.348, 0.933)
80%	(0.444, 0.975)
90%	(0.555, 0.998)
ORR (N=20)	95% CI
10%	(0.012, 0.317)
20%	(0.057, 0.437)
30%	(0.119, 0.543)
40%	(0.191, 0.639)
50%	(0.272, 0.728)
60%	(0.361, 0.809)
70%	(0.457, 0.881)

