9.7.3 Interim Analysis

The evaluation of efficacy and safety by the sponsor and investigators will occur on the initial 10 evaluable subjects while enrollment is ongoing. Based on the outcome of the evaluation the enrollment could be suspended before enrolling the planned 20 subjects in each cohort.

The EC cohort may be expanded to approximately 120 evaluable subjects. Two interim analyses will take place when 21 and 60 subjects have sufficient follow-up to be evaluated for response. The decision to expand enrollment will be based on the results of the 2 interim analyses, which will spend $\beta = 0.012$ and $\beta = 0.024$ at the first and second interim analyses, respectively. Based on an assumption of H_0 : 16% ORR and H_1 : 34% ORR, at 2-sided $\alpha = 0.02$, this design will give 97% statistical power with 120 subjects. At the first interim analysis ($N = 21$), if there are more than 3 responses, then approximately 40 additional subjects will be enrolled. At the second interim analysis ($N = 60$), if there are more than 12 responses, approximately 60 additional subjects will be enrolled. If there are 12 or fewer responses, the sponsor may decide whether to expand enrollment based on clinical outcome, eg, ORR and DOR. If the expansion beyond 60 subjects does not happen, this design for the EC cohort has approximately 86% power at 2-sided $\alpha = 0.02$.

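### The 3-of-10 response rule is mandatory in some sections and discretionary in others, and the stated EC powers hold only if it is non-binding or they are conditional on passing it; neither is stated.

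*Protocol*

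**What the plan says.** **Mandatory wording.** The Phase 2 text of the Synopsis says "For all 6 cohorts, data from the first 10 subjects in each cohort will be reviewed by the sponsor and investigators", and then "At least 3 subjects must show responses in order to determine continued enrollment to 20 evaluable subjects". EC is one of the six cohorts and is not exempted. SAP Section 3.2 carries the same two statements. Section 9.1, under Phase 2 – Expansion, says "At least 3 subjects must show response in order to determine continued enrollment up to 20 subjects".

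**Discretionary wording.** Section 9.7.2 makes growth from 10 to 20 a possibility, "depending on the evaluation by the sponsor and investigators of the efficacy and safety results". The Synopsis sample size rationale, the opening of Section 9.1 and SAP Section 4 say much the same. Footnote a to Figure 2 says that a further 10 subjects may be enrolled. Section 9.7.3 says "Based on the outcome of the evaluation the enrollment could be suspended before enrolling the planned 20 subjects in each cohort", and SAP Section 6 repeats this. None of these places gives a threshold.

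**EC power.** For a null rate of 16%, an alternative of 34% and a 2-sided alpha of 0.02, Section 9.7.2 says "this design will give 97% statistical power with 120 subjects", and gives about 86% if the cohort stops at 60. Enrollment continues with more than 3 responses at 21 subjects and more than 12 at 60; with 12 or fewer at 60 the sponsor may still expand. Table 11 shows cumulative beta of 0.012, 0.024 and 0.03 at 21, 60 and 120, with a final boundary of 0.238.

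**The concern.** A cohort with 2 responses in its first 10 has to stop under one set of sections and may continue under the other. A reader cannot tell whether continuing would be a protocol deviation.

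The EC operating characteristics depend on the answer. Table 11 allots no beta to a look at 10 subjects. If that look can stop the cohort, it adds a chance of failure under the alternative that the stated powers do not count. At stake is what the 97% and 86% describe: the whole EC design, or only the part after the first 10 subjects.

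**Working it through.** **Inputs.** All are from the documents except the final cut-offs. The EC rates are 16% and 34%. The rules are at least 3 of 10, at least 4 of 21 and at least 13 of 60. At 120 the Table 11 boundary of 0.238 means at least 29, since 28/120 = 0.233 and 29/120 = 0.242. No cut-off is given for a test at 60. I assume at least 17, because it reproduces the 86%, and show a range.

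**Step 1: the plan's own figures.** A normal approximation at 120 with the variance under the alternative gives a standard error of √(0.34 × 0.66/120) = 0.0432. Power is then Φ(0.18/0.0432 − 2.326) = Φ(1.836) = 96.7%, matching the stated 97%; so does 1 − 0.03 from Table 11. For 60 subjects, P(X ≥ 17 | 60, 0.34) = 85.7%, matching 86%. Neither calculation includes a look at 10.

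**Step 2: the 10-subject rule alone.** With X the number of responses in 10 at rate 0.34:

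P(X ≥ 3) = 1 − [0.66¹⁰ + 10(0.34)(0.66⁹) + 45(0.34²)(0.66⁸)] = 1 − (0.0157 + 0.0808 + 0.1873) = 71.6%.

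A binding rule therefore stops EC 28.4% of the time under the alternative, against a total planned beta of 3%. No later rule can bring unconditional power above 71.6%.

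**Step 3: exact power with and without the rule.** I carried the binomial distribution of cumulative responses from look to look, removing outcomes that stop the cohort.

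| Later rules applied (response rate 34%) | Without 3 of 10 | With 3 of 10 binding |
|---|---|---|
| ≥4/21, ≥13/60, ≥29/120 | 94.7% | 70.8% |
| ≥4/21, ≥29/120 (look at 60 non-binding) | 95.4% | 71.1% |
| ≥29/120 only | 99.2% | 71.3% |
| ≥17/60 only | 85.7% | 65.0% |
| ≥4/21, ≥17/60 | 84.0% | 64.9% |

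**Step 4: sensitivity to the cut-off.** Final cut-offs of 28 to 30 of 120 give 70.6% to 71.5% with the rule. At 60, with the look at 21 in place, cut-offs of 16, 17 and 18 give 88.9%, 84.0% and 77.2% without the rule and 67.7%, 64.9% and 60.6% with it.

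**Step 5: power conditional on passing.** Dividing by 0.7162 gives 0.7079/0.7162 = 98.8% at 120 (all looks binding), 0.7107/0.7162 = 99.2% with the look at 60 non-binding, and 0.6486/0.7162 = 90.6% at 60.

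**The case against.** **The stated powers may be conditional.** They belong to an expansion added by Amendment 3 for a cohort whose first formal look, at 21 subjects, lies beyond the 10-to-20 step. Given that the rule is passed, exact power is 98.8% or more at 120 and 90.6% at 60, so neither stated figure would be too high. This stands as a possible reading, and it means a reader should not infer that 97% and 86% are simply false. But no current section states the condition.

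**The rule may never have been meant to bind.** The revision history for Amendment 01 describes the 10-subject review as a consensus on the totality of the data, with no statistical interim analysis. That favours the non-binding reading, under which the EC powers are unaffected by the rule. A log entry is not operative text, however, and the requirement remains in three current places, including a SAP written to Amendment 8.

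**The two wordings might coexist.** The statistical sections do not mention the threshold, so they do not deny it; a minimum of 3 responses followed by an overall review is a workable reading. On that reading the minimum still binds, and the power question returns in full.

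**The consequence is limited.** The primary analysis is an estimate with a Clopper–Pearson interval, not a test at alpha 0.02. The Amendment 09 rationale treats the primary endpoint analysis as completed. The repair is therefore to the documentation; it cannot change enrollment.

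**Conclusion.** The text is wrong as written. The rule is a requirement in three places and a matter of judgement in seven: the Synopsis sample size rationale, the opening of Section 9.1, Figure 2 footnote a, Sections 9.7.2 and 9.7.3, and SAP Sections 4 and 6. The EC powers of 97% and 86% cannot be unconditional properties of a design in which the rule binds.

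If it binds, exact EC power falls from about 95% to about 71% at 120 subjects and from about 86% to about 65% at 60. This assumes a true rate of 34%, independent responses and the cut-offs above; the result at 120 barely moves with the cut-off or with the status of the look at 60.

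Three stronger readings are tempting and not supported:

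- A reader might set 97% against 71%. That mixes methods: 97% is an approximation or beta-spending figure, and about 95% is the like-for-like exact value.
- A reader might see the design text set against the statistical sections. The Synopsis and Section 9.1 each contain both versions.
- A reader might extend the power criticism to all six cohorts. The four cohorts with no further expansion plan have no hypothesis or power, only interval widths at 10 and 20 subjects. For them an openly stated rule at 10 is a screening choice, and printing its pass rates would be a preference.

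**What to change.** Use one rule throughout, and say whether it covers EC.

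- **Non-binding:** change the requirement to guidance in the Synopsis (Phase 2 – Expansion), Section 9.1 (Phase 2 – Expansion) and SAP Section 3.2. The rule then leaves the EC powers unaffected.
- **Binding:** align the Synopsis sample size rationale, the opening of Section 9.1, Figure 2 footnote a, Sections 9.7.2 and 9.7.3, and SAP Sections 4 and 6. Then either restate EC power as about 71% at 120 and about 65% at 60 wherever 97% and 86% appear, or say explicitly that 97% and 86% are conditional on at least 3 responses in the first 10.

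The cost is wording in two documents and, if the rule is kept binding and the powers are restated, less favourable figures. No new data or analysis is needed.
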